**6.2.2.15. Visit 16/Day 309/Week 44 (+/-3 Days)**

This visit was removed per amendment 6.

**6.2.2.16. Visit 17/Day 337/Week 48 (+/-3 Days)**

The following information will be collected:

- Concomitant medications/procedures

The following procedures and assessments will be conducted:

- Weight
- Vital signs (heart rate, blood pressure, body temperature, and respiration rate)
- IGA
- EASI
- Ophthalmology exam (select sites and patients)
- Patient assessment of pruritus intensity via IVRS/IWRS (weekly)
- Administered only to the subset of patients who speak fluently the language in which the questionnaire can be translated:
  - POEM
  - DLQI
  - EQ-5D

- Laboratory samples:
  - Hematology w/differential
  - Serum chemistry
  - ADA sample
  - Drug concentration sample
  - Urine pregnancy test – for women of childbearing potential
- If needed, counsel patient on proper dosing diary completion/reporting of each dose of study drug that is administered outside of the clinic
- Study drug dispensation/accountability
- Administer study drug

**6.2.2.17. Visit 18/Day 365/Week 52 (+/-3 Days)**

The following information will be collected:

- AEs

The following procedures and assessments will be conducted:

- Laboratory samples:
  - Urine pregnancy test – for women of childbearing potential
- Patient assessment of pruritus intensity via IVRS/IWRS (weekly)
- If needed, counsel patient on proper dosing diary completion/reporting of each dose of study drug that is administered outside of the clinic
- Study drug dispensation/accountability
- Administer study drug

**6.2.2.18. Visit 19/Day 421/Week 60 (+/-3 Days)**

The following information will be collected:

- Concomitant medications/procedures
- AEs

The following procedures and assessments will be conducted:

- Weight
- Vital signs (heart rate, blood pressure, body temperature, and respiration rate)
- IGA
- EASI

- Patient assessment of pruritus intensity via IVRS/IWRS (weekly)
- Laboratory samples:
  - Urine pregnancy test – for women of childbearing potential
- Ophthalmology exam (select sites and patients)
- If needed, counsel patient on proper dosing diary completion/reporting of each dose of study drug that is administered outside of the clinic
- Study drug dispensation/accountability
- Administer study drug

**6.2.2.19. Visit 20/Day 477/Week 68 (+/-3 Days)**

The following information will be collected:

- AEs

The following procedures and assessments will be conducted:

- Patient assessment of pruritus intensity via IVRS/IWRS (weekly)
- Laboratory samples:
  - Urine pregnancy test – for women of childbearing potential
- If needed, counsel patient on proper dosing diary completion/reporting of each dose of study drug that is administered outside of the clinic
- Study drug dispensation/accountability
- Administer study drug

**6.2.2.20. Visit 21/Day 533/Week 76 (+/-3 Days)**

The following information will be collected:

- Concomitant medications/procedures
- AEs

The following procedures and assessments will be conducted:

- Weight
- Vital signs (heart rate, blood pressure, body temperature, and respiration rate)
- Patient assessment of pruritus intensity via IVRS/IWRS (weekly)
- Ophthalmology exam (select sites and patients)
- Laboratory samples:
  - Urine pregnancy test – for women of childbearing potential

- If needed, counsel patient on proper dosing diary completion/reporting of each dose of study drug that is administered outside of the clinic
- Study drug dispensation/accountability
- Administer study drug

**6.2.2.21. Visit 22/Day 589/Week 84 (+/-3 Days)**

The following information will be collected:

- AEs

The following procedures and assessments will be conducted:

- Vital signs (heart rate, blood pressure, body temperature, and respiration rate)
- Laboratory samples:
  - Urine pregnancy test – for women of childbearing potential
- Patient assessment of pruritus intensity via IVRS/IWRS (weekly)
- If needed, counsel patient on proper dosing diary completion/reporting of each dose of study drug that is administered outside of the clinic
- Study drug dispensation/accountability
- Administer study drug

**6.2.2.22. Visit 23/Day 645/Week 92 (+/-3 Days)**

The following information will be collected:

- Concomitant medications/procedures
- AEs

The following procedures and assessments will be conducted:

- Vital signs (heart rate, blood pressure, body temperature, and respiration rate)
- Patient assessment of pruritus intensity via IVRS/IWRS (weekly)
- Laboratory samples:
  - Urine pregnancy test – for women of childbearing potential
- If needed, counsel patient on proper dosing diary completion/reporting of each dose of study drug that is administered outside of the clinic
- Ophthalmology exam (select sites and patients)
- Study drug dispensation/accountability
- Administer study drug

**6.2.2.23. Visit 24/Day 701/Week 100 (+/-3 Days)**

The following information will be collected:

- AEs

The following procedures and assessments will be conducted:

- Weight
- Vital signs (heart rate, blood pressure, body temperature, and respiration rate)
- IGA
- EASI
- Administered only to the subset of patients who speak fluently the language in which the questionnaire can be translated:
  - POEM
  - DLQI
  - EQ-5D
- Patient assessment of pruritus intensity via IVRS/IWRS (weekly)
- Laboratory samples:
  - Hematology w/differential
  - Serum chemistry
  - Urine pregnancy test – for women of childbearing potential
  - Drug concentration sample
  - ADA sample
- If needed, counsel patient on proper dosing diary completion/reporting of each dose of study drug that is administered outside of the clinic
- Study drug dispensation/accountability
- Administer study drug

**6.2.2.24. Visit 25/Day 757/Week 108 (+/-3 Days)**

The following information will be collected:

- Concomitant medications/procedures
- AEs

The following procedures and assessments will be conducted:

- Weight
- Vital signs (heart rate, blood pressure, body temperature, and respiration rate)
- Ophthalmology exam (select sites and patients)
- Patient assessment of pruritus intensity via IVRS/IWRS (weekly)

- Laboratory samples:
  - Urine pregnancy test – for women of childbearing potential
- If needed, counsel patient on proper dosing diary completion/reporting of each dose of study drug that is administered outside of the clinic
- Study drug dispensation/accountability
- Administer study drug

**6.2.2.25. Visit 26/Day 813/Week 116 (+/-3 Days)**

This visit was removed per amendment 9.

**6.2.2.26. Visit 27/Day 869/Week 124 (+/-3 Days)**

The following information will be collected:

- Concomitant medications/procedures
- AEs

The following procedures and assessments will be conducted:

- Weight
- Vital signs (heart rate, blood pressure, body temperature, and respiration rate)
- IGA
- EASI
- Patient assessment of pruritus intensity via IVRS/IWRS (weekly)
- Ophthalmology exam (select sites and patients)
- Laboratory samples:
  - Urine pregnancy test – for women of childbearing potential
  - Drug concentration sample
  - ADA sample
- If needed, counsel patient on proper dosing diary completion/reporting of each dose of study drug that is administered outside of the clinic
- Study drug dispensation/accountability
- Administer study drug

**6.2.2.27. Visit 28/Day 925/Week 132 (+/-3 Days)**

This visit was removed per amendment 9.

**6.2.2.28. Visit 29/Day 981/Week 140 (+/-3 Days)**

The following information will be collected:

- Concomitant medications/procedures
- AEs

The following procedures and assessments will be conducted:

- Vital signs (heart rate, blood pressure, body temperature, and respiration rate)
- Patient assessment of pruritus intensity via IVRS/IWRS (weekly)
- Ophthalmology exam (select sites and patients)
- Laboratory samples:
  - Urine pregnancy test – for women of childbearing potential
- If needed, counsel patient on proper dosing diary completion/reporting of each dose of study drug that is administered outside of the clinic
- Study drug dispensation/accountability
- Administer study drug

**6.2.3. Visit 30/Day 1037/Week 148 (+/-3 Days)**

The following information will be collected:

- AEs

The following procedures and assessments will be conducted:

- Vital signs (heart rate, blood pressure, body temperature, and respiration rate)
- Patient assessment of pruritus intensity via IVRS/IWRS (weekly)
- Laboratory samples:
  - Hematology w/differential
  - Serum chemistry
  - Urine pregnancy test – for women of childbearing potential
  - ADA sample
- Confirm that the patient completed/reported the dosing diary for each dose of study drug that was administered outside of the clinic
- Study drug accountability – return all PFS and study materials
- Administer study drug

**6.2.4. Visit 31/Day 1093/Week 156 through Visit 43/Day 1765/Week 252 (+/-3 Days)**

The study treatment duration will be up to 5 years. Visits 31 through 43 will occur approximately every 8 weeks until the end of treatment.

The following information will be collected:

- Concomitant medications/procedures: visit 31, 33, 35, 37, 39, 41, and 43.
- AEs
- Informed consent for the optional sub-study using the new dupilumab drug product: visit 41 or 43. See Section 6.2.6 for further information about procedures and assessments to be performed during the sub-study.

The following procedures and assessments will be conducted:

- IGA/EASI: visit 31, 37
- Weight: visit 31, 33, 35, 37, 39, 41, and 43
- Vital signs (heart rate, blood pressure, body temperature, and respiration rate): visit 31, 33, 35, 37, 39, 41, and 43
- Ophthalmology exam (select sites and patients): visit 31, 33, 35, 37, 39, 41, and 43)
- Patient assessment of pruritus intensity via IVRS/IWRS (weekly)
- Laboratory samples:
  - Hematology w/differential: visit 37
  - Serum chemistry: visit 37
  - Urine pregnancy test – for women of childbearing potential. Starting at visit 31 monthly until visit 43, urine pregnancy test must be negative before dosing.
  - ADA sample: visit 33 and 39
- Confirm that the patient completed/reported the dosing diary for each dose of study drug that was administered outside of the clinic
- Study drug dispensation/ accountability
- Administer study drug (weekly throughout the study)

**6.2.5. End of Treatment Visit/Day 1821/Visit 44/Week 260 (+/-3 Days)**

The following information will be collected:

- Concomitant medications/procedures
- AEs
- Informed consent for the optional sub-study using the new dupilumab drug product: visit 44. See Section 6.2.6 for further information about procedures and assessments to be performed during the sub-study.

The following procedures and assessments will be conducted:

- Weight
- Vital signs (heart rate, blood pressure, body temperature, and respiration rate)
- Patient assessment of pruritus intensity via IVRS/IWRS (weekly)
- IGA
- EASI
- Laboratory samples:
  - Hematology w/differential
  - Serum chemistry
  - Urine pregnancy test – for women of childbearing potential
  - Drug concentration sample
  - ADA sample
- Confirm that the patient completed/reported the dosing diary for each dose of study drug that was administered outside of the clinic
- Study drug accountability – return all PFS and study materials
- Administer study drug

**6.2.6. Sub-Study Treatment Period**

Patients who have provided written informed consent to participate in the sub-study using the new dupilumab drug product (per amendment 10) will have the following assessments and procedures performed. Patients who enter the sub-study from either visit 43 or visit 44 of the main study will have the duration of their study treatment increased by 4 or 12 weeks, respectively.

**6.2.6.1. Sub-Study Visit 1a/Day 1a/Week 0a ( $\pm 3$  days)**

Note: This visit should occur 14 days ( $\pm 3$  days) after the previous dose of current dupilumab drug product. Although, the protocol allows for a window of  $\pm 3$  days, the sponsor recommends a window  $\pm 1$  day for sub-study visit 1a after the previous dose of the current dupilumab drug product is administered.

Any redundant procedures between the main study (eg, visit 41, 43, or 44) and the sub-study (eg, visit 1a) will only be performed once.

The following information will be collected:

- Sign informed consent for sub-study
- Inclusion/exclusion criteria for switching to the new dupilumab drug product treatment (see Section 4.2.4)
- Concomitant medications/procedures
- AEs

The following procedures and assessments will be conducted:

- Weight
- Vital signs (heart rate, blood pressure, body temperature, and respiration rate)
- Ophthalmology exam (select sites and patients)
- IGA
- EASI
- Study drug dispensation/accountability
- If needed, counsel patient on proper dosing diary completion/reporting of each dose of study drug that is administered outside of the clinic
- Patient assessment of pruritus intensity via IVRS/IWRS (weekly)
- Laboratory samples:
  - Hematology w/differential
  - Serum chemistry
  - Urine pregnancy test– for women of childbearing potential
  - Drug concentration sample
  - ADA sample
- Administer study drug (new dupilumab drug product)
  - Monitor the patient for a minimum of 30 minutes after the SC injection: in addition to the predose assessments, vital signs and AE assessments will be done at 30 ( $\pm 10$ ) minutes post-injection

**6.2.6.2. Sub-Study Visit 2a/Day 29a/Week 4a ( $\pm 3$  days)**

The following information will be collected:

- Concomitant medications/procedures
- AEs

The following procedures and assessments will be conducted:

- Vital signs (heart rate, blood pressure, body temperature, and respiration rate)
- IGA
- EASI
- Laboratory samples:
  - Urine pregnancy test– for women of childbearing potential
- Administer study drug (new dupilumab study drug product)
- Patient assessment of pruritus intensity via IVRS/IWRS (weekly)
- Counsel patient on proper dosing diary completion/reporting of each dose of study drug that is administered outside of the clinic
- Study drug dispensation/accountability

**6.2.6.3. Sub-Study Visit 3a/Day 85a/Week 12a ( $\pm 3$  days)**

This visit should occur on sub-study day 85a ( $\pm 3$  days). Although the protocol allows a visit window of  $\pm 3$  days, it is strongly recommended that visit 3a occurs 14 days ( $\pm 1$  day) after the self-injection of the new dupilumab drug product on sub-study day 71a.

The following information will be collected:

- AEs
- Concomitant medications/procedures;

The following procedures and assessments will be conducted:

- Vital signs (heart rate, blood pressure, body temperature, and respiration rate)
- Ophthalmology exam (select sites and patients)
- IGA
- EASI
- Laboratory samples:
  - Hematology w/differential
  - Serum chemistry
  - Urine pregnancy test – for women of childbearing potential
  - Drug concentration sample
  - ADA sample

- Patient assessment of pruritus intensity via IVRS/IWRS (weekly)
- If needed, counsel patient on proper dosing diary completion/reporting of each dose of study drug that is administered outside of the clinic
- Study drug accountability
- Administer study drug (new dupilumab drug product)
- Study drug dispensation (Note: patients who switched at visit 41 only)

#### **6.2.6.4. Sub-Study Visit 4a/Day 169a/Week 24a ( $\pm 3$ days)**

Note: This visit is only applicable to patients who switched to the new dupilumab drug product at visit 41 of the main study.

The following information will be collected:

- AEs
- Concomitant medications/procedures;

The following procedures and assessments will be conducted:

- Vital signs (heart rate, blood pressure, body temperature, and respiration rate)
- Ophthalmology exam (select sites and patients)
- IGA
- EASI
- Laboratory samples:
  - Urine pregnancy test – for women of childbearing potential
  - Drug concentration sample
  - ADA sample
- Patient assessment of pruritus intensity via IVRS/IWRS (weekly)
- If needed, counsel patient on proper dosing diary completion/reporting of each dose of study drug that is administered outside of the clinic
- Study drug accountability
- Administer study drug (new dupilumab drug product)

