**Figure 2: Sub-Study Flow Diagram**

| Study Procedures    | Sub-Study Treatment Period |     |      |                  | End of Study  |
|---------------------|----------------------------|-----|------|------------------|---------------------------|
|                     | V1a          | V2a | V3a  | V4a  |                           |
| Sub-Study Visit (V) | V1a          | V2a | V3a  | V4a  |                           |
| Sub-Study Week (Wk) | Wk 0                       | Wk4 | Wk12 | Wk 24            | Last Dose + 12Wk          |

Abbreviations: V=visit; Wk=week.

[figure not shown]
 This optional sub-study requires a separate consent.

 Any redundant procedures with the main study visit will only be performed once.

 Applies only to patients in the sub-study who switched to the new dupilumab drug product at visit 41 of the main study. All other patients in the sub-study complete the new dupilumab drug product treatment period at sub-study visit 3a.

 The end of study (EOS) visit occurs 12 weeks after the last dose of dupilumab.

The relationship between the study visit schedules in main OLE study and the sub-study is shown in [Figure 3](#).

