## 6. STUDY SCHEDULE OF EVENTS AND VISIT DESCRIPTIONS

### 6.1. Schedule of Events

Study assessments and procedures are presented by study period and visit for the main study in [Table 1](#), [Table 2](#), [Table 3](#), [Table 4](#), [Table 5](#), [Table 6](#), and [Table 7](#). After providing informed consent for the sub-study, which is using the new dupilumab drug product, eligible patients are to follow the assessments and procedures in [Table 8](#).

In light of the public health emergency related to COVID-19, the continuity of clinical study conduct and oversight may require implementation of temporary or alternative mechanisms. Examples of such mechanisms may include, but are not limited to, any of the following: phone contact, virtual visits, telemedicine visits, online meetings, non-invasive remote monitoring devices, use of local clinic or laboratory locations, and home visits by skilled staff. Additionally, no waivers to deviate from protocol enrollment criteria due to COVID-19 will be granted. All temporary mechanisms utilized, and deviations from planned study procedures in response to COVID-19, are to be documented as being related to COVID-19 and will remain in effect only for the duration of the public health emergency.

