| Con meds/procedures  | X                          | X        | X                     | X                | X                         | X                 | X                              |
| Efficacy:m   |                            |          |                       |                  |                           |                   |                                |
| Patient assessment of pruritus intensity via IVRS/IWRS (weekly) n                               | X                          | X        | X                     | X                | X                         | X                 | X o                 |
| IGA, EASI  | X                          | X        | X                     | X                | X                         | X                 | X                              |
| Safety:m   |                            |          |                       |                  |                           |                   |                                |
| Weight   | X                          |          |                       |                  | X                         | X                 | X                              |
| Vital signs  | X                          | X        | X                     | X                | X                         | X                 | X                              |
| Ophthalmology exam (select sites and patients) p  | X                          |          | X                     |                  | X                         |                   | X q                 |
| Adverse events   | X                          | X        | X                     | X                | X                         | X                 | X                              |
| Laboratory Testing:m   |                            |          |                       |                  |                           |                   |                                |
| Hematology, chemistry  | X                          |          | X                     |                  | X                         |                   | X                              |
| Pregnancy test, WOCBP only f  | X                          | X        | X                     | X                | X                         | X                 | X                              |

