**6.2.7. End of Study Visit (84 Days After Last Dose or 12 Weeks After Last Dose)**

If the end of study assessments cannot be completed on the scheduled date (ie, 12 weeks after the last dose of dupilumab), a late visit is acceptable and is preferable to foregoing these assessments altogether; this visit should be conducted as close as possible to the scheduled date. Except as noted, the same end of study assessments are performed for patients receiving the current dupilumab drug product or new dupilumab drug product.

The following information will be collected:

- Concomitant medications/procedures
- AEs

The following procedures and assessments will be conducted:

- Weight
- Vital signs (heart rate, blood pressure, body temperature, and respiration rate)
- Ophthalmology exam (select sites and patients)
- IGA
- EASI
- Patient assessment of pruritus intensity via IVRS/IWRS (weekly)
- Laboratory samples:
  - Urine pregnancy test – for women of childbearing potential
  - Drug concentration sample
  - ADA sample
  - Hematology w/differential (patients in sub-study only)
  - Serum chemistry (patients in sub-study only)

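### Sub-study Visit 4a falls on the day of main-study Visit 44 but omits its hematology and chemistry, so the 24-week cohort has no scheduled on-drug panel after week 12a

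*Protocol*

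**What the plan says.** Patients may enter the sub-study at main-study Visit 41, 43 or 44. Once they have consented, Protocol 6.1 states that "eligible patients are to follow the assessments and procedures in" Table 8.

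The length of treatment with the new product depends on the entry visit. For Visit 4a (week 24a), Protocol 6.2.6.4 states: "Note: This visit is only applicable to patients who switched to the new dupilumab drug product at visit 41 of the main study". These patients take their last dose there (Figure 3, footnote 4). For the rest, Figure 2 says: "All other patients in the sub-study complete the new dupilumab drug product treatment period at sub-study visit 3a", which is week 12a.

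The scheduled laboratory work is as follows.

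- **Main-study Visit 44 (6.2.5 and Table 7):** "Hematology w/differential" and serum chemistry are both listed.
- **Sub-study (Table 8):** the row "Hematology, chemistry" is marked at Visits 1a and 3a, at end of study and at unscheduled visits. It is blank at Visits 2a and 4a and at early termination.
- **Visit 4a text (6.2.6.4):** the laboratory samples are the pregnancy test, drug concentration and ADA only.
- **End of study (6.2.7):** hematology and chemistry are added for sub-study patients alone.

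Table 8 takes all of these samples before the injection. On the eye exam, 6.2.6.4 lists one at Visit 4a and Table 8 has no mark there.

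**The concern.** The sub-study's primary objective is the safety of the new product (2.3), and its primary endpoint counts AESIs through the last study visit (8.2.3). Clinically symptomatic eosinophilia is one of them (7.2.3). Section 9.5.6 also carries over the laboratory summaries of 9.5.2.2: change from baseline and treatment-emergent potentially clinically significant values.

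Only Visit 41 entrants can supply laboratory values on the new product beyond week 12a, and none is scheduled. Visit 43 and 44 entrants have a panel at their last-dose visit, which for them is Visit 3a. Visit 41 entrants, with twice the treatment time, have none at theirs. Had they stayed in the main study, they would have had one on that same day.

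**Working it through.** **Inputs.** Visit 41 is week 236, Day 1653, and Visit 43 is week 252, Day 1765 (Table 6). Visit 44 is week 260, Day 1821 (Table 7). Visit 3a is Day 85a, Visit 4a is Day 169a, and end of study is last dose + 84 days (Table 8). Dosing is every 2 weeks. Study day = 7 × week + 1.

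**The plan's own figures first.** Section 6.2.6 says that entry at Visit 43 or 44 lengthens treatment by 4 or 12 weeks.

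- Visit 43: 252 + 12 = 264; 264 − 260 = 4 weeks. Agrees.
- Visit 44: 260 + 12 = 272; 272 − 260 = 12 weeks. Agrees.
- Visit 41: 236 + 24 = 260; 260 − 260 = 0. No extension is stated, which also agrees.

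**Visit 4a on the main calendar.** 1653 + (169 − 1) = 1821 = 7 × 260 + 1. This is Visit 44 exactly.

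**Interval between scheduled panels.** For this cohort end of study is Day 169a + 84 = Day 253a, main-study week 272. From Visit 3a: 253 − 85 = 168 days, or 24 weeks, of which 12 are on the new product and 12 are off drug. With the ±3-day windows at Visit 3a, at Visit 4a and at end of study, the range is (253 − 6) − (85 + 3) = 159 to (253 + 6) − (85 − 3) = 177 days. A late end-of-study visit, which 6.2.7 accepts, would lengthen it.

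**Doses covered.** Days 1a, 15a, …, 169a give 168/14 + 1 = 13 planned doses. The predose sample on Day 85a follows the six given on Days 1a to 71a. The other seven, on Days 85a to 169a, have no scheduled panel until end of study.

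**Comparison with staying in the main study, from week 236.**

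| | Scheduled hematology and chemistry |
|---|---|
| Main study | week 260 only |
| Visit 41 entrant | weeks 236 (1a), 248 (3a), 272 (end of study) |

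The sub-study patient has three panels against one. What is missing is an on-drug value late in the 24 weeks.

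**With the panel added at Visit 4a.** The 168 days split into 169 − 85 = 84 and 253 − 169 = 84. The new predose sample would follow 12 of the 13 doses.

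**The case against.** The strongest reply is that the sub-study already monitors more closely than the main study. Main-study panels after baseline are at weeks 16, 48, 100, 148, 204 and 260, which is 32 to 56 weeks apart, and amendment 6 thinned them deliberately. A 24-week interval is short by that standard. This stands: the problem is the missing on-drug value and not the spacing, and a reader who inferred that sub-study patients are monitored less overall would be wrong.

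The primary analysis is at week 12a (9.5.6), when every continuing patient has a panel. There is no hypothesis, and the eosinophilia AESI requires symptoms, which adverse event collection at Visit 4a would pick up. This also stands, and it confines the loss to the later data.

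Panels may be drawn at an unscheduled visit, so it would be wrong to infer that no safety laboratory work is possible after week 12a. Such panels are not required, however. Protocol 9.6 also places extra laboratory results in listings rather than summaries. The SAP's visit windows (SAP 6.4) would admit unscheduled values, but that SAP covers amendments 6 to 8 and predates the sub-study.

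Two further inferences are not supported. The blank early termination cell is not a defect peculiar to the sub-study: Table 7 and 6.2.8 omit the panel too, 6.2.6.5 says these visits match the main study except as noted, and withdrawing patients are asked back for end of study, which has the panel. Nor do table and text conflict on the laboratory tests: Table 8 and 6.2.6.4 agree in omitting them, so this is a design gap.

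**Conclusion.** The point holds for scheduled hematology and chemistry in Visit 41 entrants. Their last 12 weeks on the new product, and seven of 13 doses, have no scheduled panel until they are 12 weeks past the last dose. The week 12a primary analysis is not affected. The laboratory change-from-baseline and clinically-significant-value summaries lose their only scheduled on-drug values beyond week 12a, and any late AESI is assessed without a routine value beside it.

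The conclusion rests on reading Table 8 as replacing the main schedule after entry. Section 6.1 says so. Figure 3, footnote 1 requires both schedules only at Visit 1a and keeps the main schedule for patients who do not enter. No passage states outright that Visit 44 is cancelled for Visit 41 entrants.

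The number affected is unknown. The protocol says only that some of about 50 patients may be treated for 24 weeks. If the share were 20% to 60%, that would be 10 to 30 patients (0.2 × 50 to 0.6 × 50), but this share is an assumption with no source in the documents.

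The eye-exam mismatch at Visit 4a is a true contradiction between Table 8 and 6.2.6.4. It is minor, since footnote p of Table 8 limits the exam to patients in the ophthalmology sub-study, and it adds no weight to the laboratory point.

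**What to change.** Mark hematology and chemistry in the Visit 4a column of Table 8, and list hematology with differential and serum chemistry in 6.2.6.4. Blood is already taken at that visit for drug concentration and ADA, so the cost is one routine panel per Visit 41 entrant and two small edits, with no extra visit or draw. The main study already runs this panel at week 260.

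Adding the panel at early termination for sub-study patients (Table 8 and 6.2.8) is optional. It would give an on-drug value for those who leave before week 12a and remain close to their last dose, but its absence is consistent with the main study.

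Separately, make the Visit 4a ophthalmology entry agree between Table 8 and 6.2.6.4.
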